**Mucosal injury During Nasotracheal Intubation for Dental
Procedures in Children-Does the Tube Design Matter?**

Principal Investigator: [name]

April 10, 2015

1. Title: Mucosal injury during nasotracheal intubation for dental procedures in children -does the tube design matter?

2. **Investigators:** [name], [name], [name], [name], [name]

3. **Design:** Prospective randomized controlled trial

Abstract:

Extensive dental procedures in children frequently require general anesthesia due to lack of cooperation. In most cases, nasotracheal intubation (NTI) is necessary to preserve an unobstructed surgical field for the dental surgeon and to allow alignment assessment post repair. Advancing an appropriately sized breathing tube through the nares can cause significant trauma to the nasal mucosa resulting in bleeding, swelling and postoperative congestion and pain (7). Children are uniquely predisposed to these complications given the presence of adenotonsillar hypertrophy, narrow sinus passages, and friable mucosal layer (7,9). To our knowledge, there has not been any study investigating choice of nasal tracheal tube (NTT) and degree of mucosal damage in this patient population.

Background:

Several techniques have been suggested to reduce trauma during NTI, some of which are now adopted widely. These include lubrication of the nasal mucosa (17), softening of the tracheal tube by prewarming (1), and induced nasal mucosal vasoconstriction (4,5). The design of the NTT tip has been shown to impact the degree of trauma during NTI in the adult population (2,3,6,16). The Parker NTT (Parker Flex-Tip™ Tracheal Tube, Parker Medical via Mercury Medical, Clearwater, FL 33762) has a flexible distal tip that is mid line, curved and tapered. This shape theoretically facilitates its sliding past obstructions encountered in the airway such as the nasal turbinates, arytenoids and vocal cords, rather than being hung up on them and causing trauma (6). Use of Parker NTT in adult patients has been demonstrated to facilitate intubations via the fiberoptic, oral and nasotracheal pathways (2,3,6,16). While there are convincing studies in adults that demonstrate that the design of the NTT tip can impact the degree of trauma during NTI, to our knowledge no similar studies have been conducted in children.

Specific Aims:

To investigate the impact of NTT tip design on mucosal injury during NTI in children undergoing dental procedures under GA

Null Hypothesis:

Choice of NTT in children requiring NTI for dental procedures has no impact on the degree of nasal mucosal injury.

Primary Outcome:

Mucosal damage as quantified by presence and severity of bleeding immediately after passage of the NTT through the nasopharynx.

Secondary Outcomes:

Presence and degree of impingement of the NTT during NTI.

Postoperative epistaxis as defined as ongoing nasal bleeding in the recovery unit (PACU), presence of post-extubation croup in the PACU, and time to discharge from the PACU.

Research Protocol:

Inclusion criteria: children between the ages of 3-11, ASA 1-3, presenting to Wolfson's Children's Hospital (WCH) for dental procedures requiring general anesthesia with NTI.

Exclusion criteria: ASA >3, known bleeding disorder, recent or ongoing treatment with blood-thinning medicines, frequent epistaxis, active URI/congestion/rhinorrhea, craniofacial abnormalities prohibiting NTI, known difficult airway, prior nasal surgery/trauma, or allergies to any of the medicines used in this study.

Preop: eligible patients will be identified by their dentist and receive a brochure detailing the study during their dentist visit. Eligibility will be confirmed by one of the study investigators or selected research personnel (study nurse/nurse practitioner) on the day of surgery and consent obtained with the parents.

Preoperative anxiolysis will be at the discretion of the anesthesiologist, but should be limited to oral or intravenous midazolam, dexmedetomidine, or intramuscular ketamine, and not include any medicines administered intranasally.

Intraop: cases are assigned exclusively to one of the study investigators, but may involve the presence of trainees (anesthesia residents, fellows or assistants).

Induction: pre-oxygenation followed by mask induction using 6-8% Sevoflurane in Nitrous oxide/O₂ (60/40) followed by IV placement (22-24g), Fentanyl 1mcg/kg, Propofol 1-3mcg/kg, Rocuronium 0.6mg/kg.

Nasal Prep: Oxymetazoline (Afrin, Merck Consumer Care, Inc) nasal spray, 1 pump each nostril. Using the smallest pediatric sized flexible fiberoptic scope, nostril patency and degree of choanal obstruction (as defined by adenoid size, which is known to vary by patient age (8,9,10)) will be assessed avoiding tactile trauma to the nasal mucosa. Unless it is deemed not patent or significantly diminished in size, the R nostril will be preferably selected for intubation as most standard NTT are designed in favor of R-sided NTI.

NTT prep: NTT size will be chosen based on the formula 'age+16/4 -0.5' for a cuffed NTT which has been validated previously (12). For patients with Trisomy 21, the formula will be uniformly adjusted to select an NTT one size down from calculated to accommodate a smaller midface skeleton (13,14,15). Since children with Trisomy 21 make up a large part of the dental surgery population, it would be impractical to exclude them from the study. A simplified table is included below(*) to define starting NTT size for both Down syndrome and other children by age. The selected NTT will be softened in sterile warm saline (1) for at least 10min prior to insertion into the nasopharynx. Immediately prior to insertion the NTT tip will be lubricated with Lidocaine Hydrochloride USP 2% jelly (©Akorn, Incorporated | [name]).

Intubation procedure: for the purpose of this study we will intubate using the glidescope (Verathon Medical, ULC, Burnaby, BC, Canada) to mimic the standard practice of direct laryngoscopy while allowing for pictures of the oropharynx and NTT tip to be saved for later analysis. The glidescope will be inserted and positioned midline after which the prepared NTT is advanced through the selected nostril until visualization in the oropharynx. Quantification of mucosal bleeding (none, mild(blood on tracheal cuff only), moderate(blood on tracheal cuff and trace blood in the oropharynx), or severe(blood pooling in the oropharynx)) will be done at the time of intubation and verified at a later time by another study investigator based on the pictures taken. In the event of disagreement, a third investigator will make the final judgment based on the input from the prior evaluators. The presence and degree of impingement will be noted by the person intubating as follows: none (smooth passage without hang-ups), mild (single interruption in passage easily overcome by gentle rotation or angle change of the NTT), moderate (interruption in passage requiring re-passage of the tube, or more than one interruption in passage requiring readjustments) or severe (necessitating NTT down-size and/or multiple attempted re-passages). Tracheal intubation should then ensue using McGill forceps as necessary to guide the NTT through the vocal cords.

Maintenance: anesthetic gas admixture at the discretion of the anesthesiologist. Additional opioids and/or anxiolytics at the discretion of the anesthesiologist.

Postop: in the recovery unit (PACU), presence of persistent epistaxis, post-extubation croup, and the time to discharge from PACU will be noted.

Research Plan:

This will be a prospective, randomized controlled trial in children aged 3-11yrs undergoing dental procedures at WCH. We are looking to exclude the null hypothesis of no effect of NTT design by observing significant differences in the above-mentioned primary- and secondary outcome variables in the study-vs. control groups. A sample size of 80 patients (40 in each group) can detect the difference of the same magnitude between our study and control groups with a power of more than 98% at the level of significance of 0.05. Randomization to study (Parker NTT) vs. control (Standard NTT) will be computer generated and will be stratified by adenoid size. (Please refer to the Statistics Section below)

Recruitment will be facilitated by brochures handed out by our participating dental surgeons, and final enlistment will be done on the day of surgery.

Statistics Description:

Power and Sample Size Justification: The primary aim of the study is to compare the proportion of patients with the presence of at least mild (as defined in the intubation procedure section) bleeding between Parker NTT (study) and Standard NTT (control) groups. To our knowledge, no studies reported conducting research to assess the impact of mucosal injury in pediatric patients. A pediatric study (ref: El-Seify et al) reported a significant difference in the proportion of patients with the presence of bleeding between the control group (27.5%) and a similar method of our study group (7.5%). A sample size of 80 patients (40 in each group) can detect the difference of the same magnitude between our study and control groups with a power of more than 98% at the level of significance of 0.05. Randomization will be stratified by adenoid size.

Data Analysis: Collected data will be summarized by two groups. Categorical variables will be summarized by frequencies and percentages. Quantitative variables are summarized by mean and standard error of mean (SEM) or median and inter-quartile range, whichever is appropriate. A Chi-squared test or Fisher exact test will be used to compare the distribution of categorical variables, while two-sample t test or non-parametric Mann-Whitney U test will be used to compare the mean or median of quantitative variables. In addition to Chi-square/Fisher exact test, a logistic regression model will be used to compare the proportion of patients with the presence of at least mild bleeding between two groups. The analysis will be adjusted for the degree of obstruction and for other influential covariates in a multivariable logistic regression model. In addition, an ordinal logistic regression will be used to compare the severity of bleeding between two groups as long as the assumption of proportional odds met. Otherwise, a multinomial logistic regression model will be used for this purpose. The same analytical procedures will be used to compare the presence and the degree of impingement between two groups. Once again, univariable and multivariable logistic regressions will be used to compare Postoperative epistaxis and the presence of the extubation croup between two groups. Kaplan Meier survival plot and log rank test will be used to compare the distribution of time to discharge from the PACU. All tests are two-tailed at the level of significance of 0.05. The statistical software SAS, version 9.3 will be used for analyses.

Possible Discomforts and Risks: None beyond those incurred by standard practice

Possible Benefits: Identifying an easily implementable measure to reduce mucosal trauma and pain in children requiring NTL

Conflict of interest: Nothing to disclose

References:

- 1) Thermosoftening treatment of the nasotracheal tube before intubation can reduce epistaxis and nasal damage. Kim YC¹. Lee SH, Noh GJ, Cho SY, Yeom JH, Shin WJ, Lee DH, Ryu JS, Park YS, Cha KJ, Lee SC. *Anesth Analg*. 2000 Sep;91(3):698-701.
- 2) A silicone-based wire-reinforced tracheal tube with a hemispherical bevel reduces nasal morbidity for nasotracheal intubation. Kihara S¹, Komatsuzaki T, Brimacombe JR, Yaguchi Y, Taguchi N, Watanabe S. *Anesth Analg*. 2003 Nov;97(5):1488-91.

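### The picture check of the primary bleeding grade does not require a view of the cuff, and neither the second nor the third reader is masked to the arm or the bedside grade.

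*Combined protocol and SAP*

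**What the plan says.** Primary Outcome defines mucosal damage by "presence and severity of bleeding immediately after passage of the NTT through the nasopharynx". Power and Sample Size Justification fixes the cut: the arms are compared on the proportion with "presence of at least mild (as defined in the intubation procedure section) bleeding".

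Intubation procedure defines four grades. The lowest positive grade is "mild(blood on tracheal cuff only"; moderate adds a trace of blood in the oropharynx, and severe is pooling there. The same section gives the reading process:

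- Grading "will be done at the time of intubation and verified at a later time by another study investigator based on the pictures taken". No person is named for the bedside grade, whereas impingement is assigned to whoever intubates.
- The pictures come from the video laryngoscope, whose use is justified as "allowing for pictures of the oropharynx and NTT tip to be saved for later analysis".
- If the two disagree, "a third investigator will make the final judgment based on the input from the prior evaluators".

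Background describes the study tube by its distinctive distal tip, and Specific Aims names tip design as the factor under study. The standard tip is not described. No section mentions masking, coding or cropping of pictures, or withholding the arm or the bedside grade from a later reader.

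**The concern.** At the cut that defines the primary endpoint, the deciding evidence is blood on the cuff. The only description of the verification pictures names the oropharynx and the tip. A frame may well include the cuff, and the fact that the grade is to be verified implies that such a view is wanted, but the plan does not require it. The structure that is named, the tip, is the one that may identify the arm.

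The bedside grade is probably given with the tube in view, so the picture reading is the most practical step at which to mask. The plan does not use that opportunity. To verify a grade is not necessarily to give an independent one: the second reader may know the bedside grade and the arm, and the third works from what the first two supply. If the bedside grade leaned towards one tube, the later readings as written might confirm the lean instead of correcting it. What is at stake is the validity of the primary comparison in a trial of 40 children per arm.

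**Working it through.** **The texts side by side.** The endpoint is cut between none and mild. Mild is cuff blood alone. The pictures are described by oropharynx and tip. The tip is the intervention. No reader is masked. The gap in the plan follows from these statements alone. The arithmetic below only shows what a lean of a given size would do.

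**Inputs from the plan.** 40 per arm; rates of 27.5% (control) and 7.5% (study) from Power and Sample Size Justification; two-sided 0.05. Data Analysis allows either test: "A Chi-squared test or Fisher exact test will be used to compare the distribution of categorical variables". Results are therefore given as chi-squared / Fisher, without continuity correction. The tilts, the regraded calls and the miss rate are assumptions.

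**Plan's own figure.** The plan states power above 98% for these rates. Exact enumeration gives 68.9% / 58.5%, so the figure does not reproduce. That is a separate matter. The recomputed values serve here only as the baseline for step 3.

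**Step 1. Effect of a lean on type I error.** Let the true rate be 27.5% in both arms. One call in 40 is 1/40 = 2.5 percentage points. For observed rates a and b, the rejection probability is the sum over all x and y of Bin(x; 40, a) × Bin(y; 40, b), taken where the test gives p ≤ 0.05.

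| Assumed tilt | Observed rates | Chi-squared / Fisher |
|---|---|---|
| None | 27.5% vs 27.5% | 4.9% / 2.9% |
| One call per arm, opposite directions | 30.0% vs 25.0% | 7.8% / 4.9% |
| Two calls per arm, opposite directions | 32.5% vs 22.5% | 16.7% / 11.7% |

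Of these cases, only two calls per arm takes the error above 10%.

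**Step 2. General fragility (not evidence of a lean).** The expected bleeds are 0.275 × 40 = 11 and 0.075 × 40 = 3. With q = (x + y)/80, z = [(x − y)/40] / √[q(1 − q) × 2/40]. For 11 vs 3, q = 0.175 and z = 0.200/0.0850 = 2.354.

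| Bleeds, control vs study | z | p, chi-squared / Fisher |
|---|---|---|
| 11 vs 3 | 2.354 | 0.019 / 0.037 |
| 10 vs 3 | 2.121 | 0.034 / 0.066 |
| 11 vs 4 | 2.005 | 0.045 / 0.083 |
| 10 vs 4 | 1.765 | 0.078 / 0.140 |

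One regrade in one arm stays significant by chi-squared but not by Fisher. One in each arm, both towards no difference, loses significance by both.

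**Step 3. Cost of reading from stills alone.** If stills missed an assumed 20% of bleeds in both arms, the rates become 0.8 × 27.5% = 22.0% and 0.8 × 7.5% = 6.0%. Exact power then falls from 68.9% to 57.9% (chi-squared) and from 58.5% to 44.1% (Fisher).

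**The case against.** The strongest reply is that the plan already has two readings, saved images and a tie-break, and that no bias is shown. Both parts stand. The readings are a real safeguard, and nothing in the documents measures a lean.

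The words about the pictures also explain why the device is used; they are not a list of required or excluded views. Read with the grading rule, they suggest that the pictures are meant to support a cuff-based grade. So a reader might infer that the later investigators will be unable to see the cuff. The documents do not support that, only that the view is not required. Nor do they say what share of bleeds would be cuff-only.

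Two other stronger readings go too far:

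- A reader might infer that the picture reading is the only point at which the arm could be hidden. No bedside grader is named for bleeding, so the text does not establish this. That the tip is recognisable in a still is likewise an inference.
- A reader might take step 2 to mean that single cases decide the trial, or that bias is present. One regrade in one arm remains significant by chi-squared, and the same movement would follow random error by fully masked readers. It reflects the small sample.

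Finally, the remedy below still gives the third reader the bedside grade, so its protection of the primary result is partial. That is true, and it is accepted because stills may miss blood seen live.

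**Conclusion.** The point holds as a gap in how the primary endpoint is verified. A cuff view is not required, the tip may reveal the arm, and neither later reader is masked to the arm or to the bedside grade. It should be corrected because the correction is cheap and bears on the primary comparison, not because bias has been demonstrated.

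The size of any lean is unknown. Under the assumed tilts, one call per arm changes the long-run error modestly, and two calls per arm surviving verification would be serious. A reader might infer that the trial's error rate is 16.7%. That figure belongs to an assumed net tilt of four calls, for which the documents give no evidence. The conclusion rests on the absence of any masking statement in the plan and on the inference that the two tips can be told apart in a picture.

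**What to change.** Use the readers already planned.

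1. Require a saved frame that shows the cuff as well as the oropharynx.
2. Code the frames, and crop or cover the tip where the cuff stays readable. Flag frames where this is not possible and report their number by arm.
3. Have the second investigator, who should not have been present at that case, grade the frames independently, without the arm or the bedside grade.
4. If the grades differ, the third investigator decides from the frames and both grades, without being told the arm or who gave which grade.
5. Keep the adjudicated grade as primary. Report agreement between bedside and masked grades by arm, and repeat the primary analysis with the masked picture-only grade as a sensitivity analysis.

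The picture-only grade should not become primary, because the outcome is bleeding straight after the tube passes and a still may not capture it.

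**Cost.** One more saved frame and some image handling per case, a wording change, and no added readers. Masking will be incomplete for some frames. A lean can still enter where the third investigator sides with the live grade; the sensitivity analysis can help to show this but does not remove it. That analysis also loses power if stills miss bleeds, as in step 3 of the working.

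### The stated power of more than 98% is wrong: 40 per arm gives about 58–69% for 27.5% vs 7.5%

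*Combined protocol and SAP*

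**What the plan says.** Under Power and Sample Size Justification in the Statistics Description, the primary aim is given as follows: "compare the proportion of patients with the presence of at least mild (as defined in the intubation procedure section) bleeding", for the Parker tube against the standard tube. The effect size is borrowed from a paediatric study with bleeding in 27.5% of controls and 7.5% of the comparison group. On the number of patients, the plan states: "A sample size of 80 patients (40 in each group) can detect the difference of the same magnitude". The power that it attaches to this detection claim reads: "between our study and control groups with a power of more than 98% at the level of significance of 0.05". The Research Plan section carries the same sentence.

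The Data Analysis section names a chi-squared or Fisher exact test for categorical variables, with logistic regression in addition, and adds: "All tests are two-tailed at the level of significance of 0.05". The plan names no power formula or software, and it gives no other effect size and no allowance for losses.

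**The concern.** A 20-point difference with 40 per arm is a modest comparison, and 98% looks too high on sight. If the trial observed exactly its planning rates, 11/40 vs 3/40, the p-value would be 0.019 by uncorrected chi-squared and 0.037 by Fisher. A result that falls only a little inside 0.05 when the estimate equals the target cannot go with 98% power, because ordinary sampling variation would often carry it across the threshold.

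This is the only justification given for the sample size, and it concerns the primary comparison. Power above 98% implies a type II error below 2%. The null hypothesis is that tube choice has no impact on mucosal injury. A reader who trusts the stated power could take a non-significant result as near-proof of that, when the trial had a substantial chance of missing the effect it was designed to find.

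**Working it through.** **Inputs, all from the plan.** Control rate p1 = 0.275, study rate p2 = 0.075, n = 40 per arm (Power and Sample Size Justification); two-sided 0.05, chi-squared or Fisher (Data Analysis). No dropout is assumed.

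**Attempt to reproduce the stated figure: pooled normal approximation.**

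Mean rate = (0.275 + 0.075)/2 = 0.175.

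z = [(p1 − p2)√n − 1.96·√(2 × 0.175 × 0.825)] / √(0.275 × 0.725 + 0.075 × 0.925)

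= [0.20 × 6.325 − 1.96 × 0.5374] / √(0.1994 + 0.0694)

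= (1.265 − 1.053) / 0.518 = 0.41

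Power = Φ(0.41) = 65.9%. The stated figure is not reproduced.

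**Other methods, two-sided 0.05, 40 per arm.** The exact figures sum the binomial probabilities of all 41 × 41 possible outcomes in which the test rejects.

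| Method | Power |
|---|---|
| Pooled normal | 65.9% |
| Unpooled normal | 68.4% |
| Arcsine (h = 0.549; Φ(0.549·√20 − 1.96)) | 69.0% |
| Exact, uncorrected chi-squared | 68.9% |
| Exact, Fisher | 58.5% |
| Exact, Yates-corrected chi-squared (not named in the plan) | 53.6% |

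For the tests that the plan names, the type II error is about 31% (100 − 69.0) to 42% (100 − 58.5).

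**Readings that might rescue 98%.**

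| Reading | Power |
|---|---|
| One-sided 0.05, pooled normal | 76.9% |
| 80 per arm, two-sided, pooled normal | 92.2% |
| 80 per arm and one-sided, pooled normal | 96.0% |
| Most favourable 20-point gap (20% vs 0%), 40 per arm | 86.1% |
| Same odds ratio at its most favourable base rate, 40 per arm | 92.3% |
| One-sample, one-sided test of 40 against a fixed 27.5% | 97.8% |

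None exceeds 98%. The last comes closest and may be where the figure came from, but that is a guess, and it is not the planned two-group, two-tailed comparison.

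**What 98% would require.** With the pooled formula,

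n per arm = [1.96 × 0.5374 + z(power) × 0.5184]² / 0.20²

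- 80% (z = 0.842): 55.5, so 56 per arm (66 with continuity correction)
- 90% (z = 1.282): 73.8, so 74 per arm (84)
- 98% (z = 2.054): 112.1, so 113 per arm (122)

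Alternatively, 40 per arm gives 98% if the control rate is about 45.5% against 7.5%.

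**What 40 per arm detects with about 80% power, against 7.5%.** A control rate of 32% gives 79.7% (pooled normal), 82.5% (exact chi-squared) and 75.0% (Fisher). With Fisher about 34% is needed (80.8%).

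**The case against.** The strongest defence lies in the loose phrase "can detect the difference of the same magnitude between our study and control groups". If it means the same risk ratio, 98% can be reached with 40 per arm, but only at a control rate of about 56.5% (against 15.4%), which appears nowhere in the plan. Read as the same absolute difference or the same odds ratio, it cannot reach 98% at any base rate.

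The ordinal severity analysis or covariate adjustment might have different power. Neither was modelled here. The plan ties its power statement to the binary endpoint of at least mild bleeding and gives no severity distribution from which an ordinal calculation could be made.

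Three points on the other side do stand. First, the error leaves the endpoint, tests, significance level and randomisation as they are, and it affects neither the type I error nor the effect estimate. The harm is confined to the justification of N and the reading of a null result. Second, nothing in the plan says that a non-significant result will be presented as evidence of no effect, so this is a risk and not a stated intention. Third, whether to keep 80 patients or enlarge the trial is the sponsor's choice, and the documents do not show whether enrolment had begun.

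**Conclusion.** The concern holds. For 27.5% vs 7.5% with 40 per arm at two-sided 0.05, power is about 66–69% with chi-squared and about 58% with Fisher. The stated figure is too high by roughly 30 to 40 percentage points. The chance of missing the target effect is about one in three with chi-squared and about two in five with Fisher, against the one in fifty that the plan implies. The result rests only on figures printed in the plan. It assumes independent binomial outcomes, equal groups and no losses; any loss would lower power further.

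**What to change.** Correct the power sentence in both places (Research Plan; Power and Sample Size Justification) and name the test each figure belongs to. If N stays at 80, for example:

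> With 40 per group and a two-sided significance level of 0.05, the power to detect 27.5% vs 7.5% is about 66% by the pooled normal approximation for the chi-squared test (69% by exact enumeration) and about 58% with Fisher's exact test. Power of about 80% is reached for 32% vs 7.5% with the chi-squared test and for 34% vs 7.5% with Fisher's exact test.

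Add to Data Analysis that the primary comparison will be reported as a risk difference with a 95% confidence interval, and that a non-significant result will not be presented as evidence of no impact. This addition goes beyond correcting the arithmetic, but it guards against the misreading that the wrong figure invites.

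The cost is a few sentences and a less favourable stated power, with no extra patients. If recruitment is still open and the sponsor wants 80% power for the original target, the alternative is 56 per arm, 112 in total (66 per arm, 132 in total, with continuity correction), which does add patients.

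### The bleeding-severity test is picked by an unspecified proportional-odds check on the trial's own data; depending on the unnamed test statistic, the rule is liberal (about 6–11%) or slightly less powerful

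*Combined protocol and SAP*

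**What the plan says.** The Primary Outcome section includes severity as well as presence: "Mucosal damage as quantified by presence and severity of bleeding immediately after passage of the NTT through the nasopharynx". The Intubation procedure section grades bleeding as none, mild, moderate or severe.

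For severity, Data Analysis plans that "ordinal logistic regression will be used to compare the severity of bleeding between two groups as long as the assumption of proportional odds met". If it is not met: "Otherwise, a multinomial logistic regression model will be used for this purpose". The plan gives no test or cut-off for the check, no statistic (likelihood-ratio, score or Wald) for the tube effect in either model, and no handling of empty cells. The nearest thing to a cut-off is the general statement that "All tests are two-tailed at the level of significance of 0.05".

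Three other sentences in Data Analysis bear on the point:
- A general one also reaches the four grades: "A Chi-squared test or Fisher exact test will be used to compare the distribution of categorical variables". It does not say which severity p-value leads.
- Descriptive grade tables are already planned: "Categorical variables will be summarized by frequencies and percentages".
- The rule extends to a second scale: "The same analytical procedures will be used to compare the presence and the degree of impingement between two groups".

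**The concern.** A test chosen by looking at the same data does not keep the error rate of either component. Tables that fail a proportional-odds check tend to be those in which the arms differ in some irregular way, and these are the tables in which a 3-df multinomial test is likely to reject. The rule can therefore exceed 5% even when each test alone is sound.

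The fallback also arrives when data are thin. At the planning rates the expected number of bleeders is 40 × 0.275 = 11 in the control arm and 40 × 0.075 = 3 in the Parker arm. Three patients cannot reliably fill three bleeding grades, and a grade seen in one arm but absent from the other makes a multinomial odds ratio zero or infinite. Likelihood-ratio and Wald tests then part company sharply, so leaving the statistic open nearly leaves the answer open in those trials. Severity is in the primary outcome wording, so its p-value will be read as more than descriptive.

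**Working it through.** **The plan's own figure.** The documents give no error rate or power for the severity analysis. Their only operating figure is power above 98% for any bleeding (Power and Sample Size Justification). With 40 per arm, 27.5% vs 7.5%, two-sided 0.05 and pooled rate 0.175:
- SE under the null = √(2 × 0.175 × 0.825 / 40) = 0.0850
- SE under the alternative = √((0.275 × 0.725 + 0.075 × 0.925) / 40) = 0.0820
- power = Φ((0.20 − 1.96 × 0.0850) / 0.0820) = Φ(0.41) ≈ 66%

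The 98% is not reproduced. That is a separate matter, and nothing below depends on it.

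**Simulation set-up.** From the documents: 40 per arm, four grades, 27.5% vs 7.5%, two-sided 0.05. Assumed: the mild/moderate/severe split among bleeders (equal thirds, 50/30/20, 60/30/10, 70/25/5, 80/15/5), and a proportional-odds check at 0.05 by score or likelihood-ratio (LR) test. If the check passes, the 1-df ordinal test is used; otherwise the multinomial test. Most settings used 20,000 trials, some 4,000 to 8,000. Monte Carlo SE for an error rate is about 0.2 points at 20,000 (√(0.08 × 0.92 / 20,000)) and 0.4 at 4,000 (√(0.07 × 0.93 / 4,000)). Models are unadjusted except where stated; covariates would thin the data further.

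**False positives, no tube effect, common bleeding rate 17.5–50%**

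| Rule | Size |
|---|---|
| Two-step, LR tests | 6.8–11.0% |
| Two-step, score tests | 6.0–7.8% |
| Two-step, Wald tests | 3.5–6.4% |
| Ordinal LR alone | 5.1–6.0% |
| Multinomial LR alone | 4.9–8.4% |
| Fisher on four grades | 4.2–4.9% |
| Stratified Wilcoxon | 4.6–5.2% |
| Ordinal LR adjusted for adenoid size | 5.4–6.0% |

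The last two rows assume three equal adenoid strata. The lowest two-step LR figures (6.8–7.0%) belong to the 80/15/5 split at a 17.5% rate. At rates of 7.5% and 75% the two-step LR figure is 8.4–10.4%, but at 7.5% the ordinal LR test alone is already at 7.4–7.8%.

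**What the switch itself adds.** Size of the rule = ordinal size + P(switch) × [P(multinomial rejects | switch) − P(ordinal rejects | switch)]. A 75% bleeding rate with equal thirds is a clean case: no empty grades, ordinal LR alone 5.3%, multinomial LR alone 5.4%. The score check fires in 5.3% of trials. Then 5.3 + 0.053 × (62.0 − 4.5) = 5.3 + 3.0 = 8.3%, against 8.4% simulated. Both tests are near nominal, so here the excess comes from the switch. In sparser settings the multinomial LR test is itself liberal, and the excess has both sources.

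**Planning rates, same split or proportional odds**
- Switch fires: 4–8% of trials.
- A grade seen in one arm and absent from the other: 74–81% of all trials; 89–99% of switched trials for the three splits where this was tabulated.
- Within switched trials: multinomial LR rejects in about 91–99%, multinomial Wald in 0.2–20%.
- Power, LR: ordinal alone 69–70%, two-step 71–72%.
- Power, Wald: ordinal alone 59–60%, two-step 54–58%.

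The same identity reproduces these. For 80/15/5 with a score check (switch 7.6%):
- Wald: 59.1 − 0.076 × (74.6 − 18.8) = 54.9% (simulated 54.8%)
- LR: 69.3 + 0.076 × (98.5 − 82.8) = 70.5% (simulated 70.5%)

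The gap between LR and Wald within the ordinal model is 69.3 − 59.1 = 10.2 points, larger than anything the switch does here.

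**If proportional odds truly fails.** In three assumed patterns at the same rates, the switch fires in 40–65% of trials. Wald then rejects in 0–14% of switched trials and LR in 98–100%. Overall Wald power falls from 51–65% (ordinal alone) to 18–41% (two-step).

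**The case against.** **What stands**
- The fallback is written down in advance, and moving to another model when proportional odds fails is a recognised approach.
- The two harms are alternatives. A reader might infer that the plan suffers inflated error and a powerless fallback together. It cannot: the first needs LR or score tests, the second Wald tests, and the documents choose none of them.
- The sizes depend on assumed grade splits, and part of the LR excess is small-sample error of the multinomial test.
- A reader might infer a large loss of power. When the grade mix is similar in both arms the switch moves power by only 1–2 points up (LR) or 2–5 points down (Wald). The larger LR–Wald gap arises inside the ordinal model.
- A reader might infer that the primary comparison is compromised. Power and Sample Size Justification sets the primary aim as the proportion with at least mild bleeding. That is tested by chi-squared or Fisher and by binary logistic regression, and the ordinal model is added to these.
- Fisher's test on the four grades is already planned and holds its size.
- Nothing shows that impingement grades will be sparse.

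**What does not stand**
- The inflation is not only a small-sample artefact: it appears where no grade is empty and both component tests are near 5%.
- It is not peculiar to LR tests, since score tests throughout still give about 6–8%.
- Fisher's presence does not settle the matter, because no severity p-value is named as leading. Claiming success on either ordinal LR or Fisher gives 7.2–8.4%.

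**Conclusion.** The point holds in a limited form. As written, the severity rule is either liberal (about 7–11% with LR tests, 6–8% with score tests, against about 5–6% for the ordinal model alone) or, with Wald tests, near nominal size but 2–5 points less powerful at the planning rates. This assumes a check at 0.05, the splits listed, common bleeding rates of 17.5–50% for size, and similar grade mixes in the two arms for power. Importance is minor to moderate: severity is named in the primary outcome, but neither the sample size nor the yes/no bleeding test rests on it. The documents do not support calling this a flaw in the powered comparison, or extending the sparsity argument to impingement.

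**What to change.** Drop the data-driven switch for inference and name one severity test, whatever a proportional-odds check shows. Either of these would do:

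> Severity of bleeding will be tested with a two-sided Wilcoxon rank-sum test stratified by adenoid size.

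> Severity of bleeding will be tested with the likelihood-ratio test for tube in a proportional-odds model adjusted for adenoid size.

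The Wilcoxon test keeps its size (4.6–5.2%) and gives up 2–3 points of power; the adjusted LR test is slightly liberal (5.4–6.0%). Adenoid size is the stratification factor, and the plan already adjusts for the obstruction it defines: "The analysis will be adjusted for the degree of obstruction and for other influential covariates in a multivariable logistic regression model".

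With either test, report the common odds ratio with a profile-likelihood interval, described as an average across cut-points. Show the already planned grade frequencies by arm, so that any non-proportional pattern is visible. Label Fisher's test on the four grades, and any multinomial model, as supportive. State how an infinite estimate will be reported: the Parker arm has no bleeds with probability 0.925^40 = 4.4% at the planning rate. Use the same rule for degree of impingement, for consistency only.

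**Cost.** A few sentences; no extra data or patients. The real downside is a tube effect on the mix of grades alone. At 27.5% bleeding in both arms, the ordinal LR test then has about 7–10% power, and a rank test would likewise have little. The two-step rule has 39–96% with LR tests (at inflated size) and 6–11% with Wald. The supportive Fisher test recovers most of this (32–94%) at correct size. It has only 51–56% power at the planning rates, so it should lead only if a mix-only effect is the main interest.
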